SAP Amendment 1	01 Jun 2022	Amendment 1 (15 March 2022)	The SAP was amended to align to changes performed in the Protocol Amendment 1.	This amendment is considered substantial based on the criteria defined in Article 10(a) of Directive 2001/20/EC of the European Parliament and the Council of the European Union because it significantly impacts the safety of participants, conduct of the trial and scientific value of the trial.

1. INTRODUCTION

The purpose of this SAP is to describe the planned analyses to be included in the CSR for Study 214725 (RSV MAT-012). Details of the planned interim analysis, as well as the final analyses, are provided.

1.1. Objectives, Estimands and Endpoints

Table 1 Study objectives, estimands and endpoints

Objectives	Endpoints & Estimands
Primary	

Safety assessment:
 
Maternal participants:
 
 • To evaluate the safety and reactogenicity of a single IM dose of study intervention (RSV maternal vaccine or placebo) administered to maternal participants up to 42 days post-delivery. • To evaluate the pregnancy outcomes and pregnancy-related AESIs up to 42 days post-delivery, in maternal participants who received a single IM dose of study intervention (RSV maternal vaccine or placebo). 	
 • Number and percentage of maternal participants reporting: 
 – Solicited administration site and systemic events during a 7-day follow-up period after dosing (i.e. Day 1 to Day 7 included). – Unsolicited AEs that occur during a 30-day follow-up period after dosing (i.e. Day 1 to Day 30 included). – SAEs, (S)AEs leading to study withdrawal and MAEs from Day 1 up to 42 days post-delivery. • Number and percentage of maternal participants reporting: 
 – Pregnancy outcomes * from Day 1 up to 42 days post-delivery. 
 * These include live birth with no congenital anomalies, live birth with minor congenital anomaly(ies) only; live birth with at least one major congenital anomaly, fetal death/still birth (antepartum or intrapartum) with no congenital anomalies, fetal death/still birth (antepartum or intrapartum) with only minor congenital anomalies, fetal death/still birth (antepartum or intrapartum) with at least 1 major congenital anomaly; elective/therapeutic termination with no congenital anomalies; elective/therapeutic termination with only minor congenital anomalies, and elective/therapeutic termination with at least 1 major congenital anomaly¹. – Pregnancy-related AESIs * and worsening of pre-existing medical conditions and/or obstetric complications from Day 1 up to 42 days post-delivery. 
 * These include maternal death, hypertensive disorders of pregnancy (gestational hypertension, pre-eclampsia, pre-eclampsia with severe features including eclampsia), fetal growth restriction, gestational diabetes mellitus, pathways to preterm birth (premature preterm rupture of membranes, preterm labor, provider-initiated preterm birth) and chorioamnionitis.¹

CONFIDENTIAL

[figure not shown]
Objectives	Endpoints & Estimands

Infant participants:
 
 To evaluate safety up to 42 days post-birth in infants born to maternal participants who received a single IM dose of study intervention (RSV maternal vaccine or placebo). 	
 Number and percentage of infant participants reporting: 
 Neonatal / infant AESIs * from birth up to 42 days post-birth. * These include small for gestational age, low birth weight including very low and extremely low birth weight (<2500 g, <1500g, <1000g), congenital anomalies (major external structural defects, internal structural defects, functional defects), neonatal death (in an extremely preterm birth [22≤GA<28 weeks], in a preterm live birth [28≤GA<37 weeks], or in a term live birth) and preterm birth.¹ SAEs, (S)AEs leading to study withdrawal and MAEs from birth up to 42 days post-birth.

 To evaluate safety up to 365 days post-birth (1 year of age) in infants born to maternal participants who received a single IM dose of study intervention (RSV maternal vaccine or placebo). 	
 Number and percentage of infant participants reporting: 
 SAEs, (S)AEs leading to study withdrawal and MAEs from birth up to 180 days post-birth. SAEs, (S)AEs leading to study withdrawal and MAEs from birth up to 365 days post-birth.

Immunogenicity assessment:
 
Maternal participants:
 
 To evaluate the immunogenicity of a single IM dose of study intervention (RSV maternal vaccine or placebo) administered to maternal participants, at delivery. 
Cord blood/ placental transfer:
 
 To evaluate the transfer of RSV-specific antibodies from maternal participants who received a single IM dose of study intervention (RSV maternal vaccine or placebo) to their infants at delivery. 
Infant participants:
 
 To evaluate the RSV-specific antibody levels at birth in infants born to maternal participants who received a single IM dose of study intervention (RSV maternal vaccine or placebo). 	
 Humoral immune responses at pre-dosing (Day 1) and at delivery: 
 RSVPreF3 IgG-specific antibody concentrations Neutralizing antibody titers against RSV-A Ratio between cord blood* and maternal RSVPreF3 IgG-specific antibody concentrations at delivery *or infant blood sample collected within 72 hours after birth (if no cord blood sample can be obtained). Humoral immune responses at delivery*: 
 RSVPreF3 IgG-specific antibody concentrations Neutralizing antibody titers against RSV-A *Measured in cord blood sample collected at delivery or in infant blood sample collected within 72 hours after birth (if no cord blood sample can be obtained).
Secondary	

Safety assessment:
 
Maternal participants:
 
 To evaluate the safety of a single IM dose of study intervention (RSV maternal vaccine and placebo) administered to maternal participants, up to 180 days post-delivery. 	
 Number and percentage of maternal participants reporting: 
 SAEs, (S)AEs leading to study withdrawal and MAEs from Day 1 up to 180 days post-delivery.

CONFIDENTIAL

Objectives	Endpoints & Estimands

 To evaluate the worsening of pre-existing medical conditions and/or obstetric complications up to 180 days post-delivery, in maternal participants who received a single IM dose of study intervention (RSV maternal vaccine or placebo). To evaluate the occurrence of RSV-associated MA-RTIs in maternal participants who received a single IM dose of study intervention (RSV maternal vaccine and placebo) up to 180 days post-delivery. 	
 Number and percentage of maternal participants reporting: 
 Worsening of pre-existing medical conditions and/or obstetric complications from Day 1 up to 180 days post-delivery. Number and percentage of maternal participants reporting: 
 RSV-associated MA-RTIs from Day 1 up to 180 days post-delivery.

Infant participants:
 
 To evaluate the occurrence of medically assessed, RSV-associated LRTIs up to 365 days post-birth (12 months of age) in infants born to maternal participants who received a single IM dose of study intervention (RSV maternal vaccine or placebo). To evaluate the occurrence of medically assessed, RSV-associated hospitalization up to 365 days post-birth (12 months of age) in infants born to maternal participants who received a single IM dose of study intervention (RSV maternal vaccine or placebo). 
Immunogenicity assessment:
 
Maternal participants:
 
 To evaluate the immunogenicity of a single IM dose of study intervention (RSV maternal vaccine or placebo) administered to maternal participants up to delivery. 
Infant participants:
 
 To evaluate neutralizing antibody titers against RSV-B at birth in infants born to maternal participants who received a single IM dose of study intervention (RSV maternal vaccine or placebo). 	
 From birth up to 365 days post-birth (12 months of age), number and percentage of infant participants reporting medically assessed, RSV-associated LRTIs of any severity and severe RSV-associated LRTIs (according to the cases definitions). From birth up to 365 days post-birth (12 months of age), number and percentage of infant participants reporting medically assessed, RSV-associated hospitalizations (according to the cases definitions). Humoral immune responses at Day 31 post-dosing: 
 RSVPreF3 IgG-specific antibody concentrations Neutralizing antibody titers against RSV-A Humoral immune responses at pre-dosing (Day 1), at Day 31 post-dosing and at delivery: 
 Neutralizing antibody titers against RSV-B Humoral immune responses at delivery*: 
 Neutralizing antibody titers against RSV-B 
* Measured in cord blood sample collected at delivery or infant blood sample collected within 72 hours after birth (if no cord blood sample can be obtained).

CONFIDENTIAL

Objectives	Endpoints & Estimands

 To evaluate RSV-specific antibodies up to Day 181 post-birth (6 months of age) in infants born to maternal participants who received a single IM dose of study intervention (RSV maternal vaccine or placebo). 	
 Humoral immune responses at Day 43*, at Day 121* and at Day 181*: 
 – RSVPreF3 IgG-specific antibody concentrations – Neutralizing antibody titers against RSV-A and RSV-B 
* Measured in infant blood samples collected at Day 43 (sub-cohort 1, V2-NB), at Day 121 (sub-cohort 2, V3-NB) and at Day 181 (sub-cohort 3, V4-NB) post-birth. Each infant will be randomly assigned (1:1:1) to one of 3 sub-cohorts.

Tertiary	

AE = adverse event; **IM** = intramuscular; **AESI** = adverse event of special interest; **LRTI** = lower respiratory tract illness; **MAE** = medically attended adverse event; **NB** = newborn; **RSV** = respiratory syncytial virus; **RSV-A/B** = respiratory syncytial virus subtype A/B; **MA-RTI** = medically attended respiratory tract illness; **RSVPreF3 IgG** = respiratory syncytial virus PreF3 immunoglobulin G; **SAE** = serious adverse event; **GMT** = Geometric mean titer; **GMC** = Geometric mean concentration

[figure not shown]
¹ Maternal and neonatal AESI and pregnancy outcomes should be recorded in the eCRF along with assessment of level of diagnostic certainty by Global Alignment of Immunization Safety Assessment in pregnancy (GAIA) definitions when applicable. Of note, some events of interest fall under a single category but have multiple subcategories. For example, hypertensive disorders of pregnancy is an event with 3 subcategories that include: 1) gestational hypertension; 2) pre-eclampsia; and 3) pre-eclampsia with severe features (including eclampsia). For each event, the investigator should identify the event and select the applicable sub-category.

1.2. Study Design

Overview of Study Design and Key Features

Figure 1 and Figure 2 provide overviews of the study design for maternal and infant participants, respectively.

Figure 1 Study design overview – Maternal participants

MAE = medically attended adverse event; **MA-RTI** = medically attended respiratory tract illness; **(S)AE** = (serious) adverse event; **SCR** = screening

¹ Visit 2 (Day 31) may be replaced by Visit 3 (Delivery) in case of premature delivery. If the delivery date occurs prior to Day 31 post-study intervention, there will be no Visit 2 (Day 31).

² SAEs related to study participation are to be collected from screening to Visit 1 (Day 1 pre-study intervention).

³ Following study intervention (RSV maternal vaccine or placebo) administration, SAEs and (S)AEs leading to study withdrawal are to be collected from Day 1 (Visit 1) up to 180 days post-delivery (Contact 2).

⁴ If not performed as part of the routine care, the blood and urine samples for screening should be collected within 15 days prior to study intervention administration.

⁵ **Due to the recent safety signal in RSV-MAT-009, there will be no further enrollment and vaccination of maternal participants. Refer to Protocol section 2.3 for further details.**

[figure not shown]
⁶ **Due to the change in the study requirements, MA-RTIs experienced by the maternal participants will no longer be collected.**

⁷ **In addition to the monthly contacts between Visit-2 and the Delivery visit, additional not pre-specified contacts and/or visits can be made more often (at any desired frequency), as per investigator's, maternal participant's or LAR's discretion.**

Note: Placenta samples will be collected at delivery from all maternal participants, whenever feasible. These samples may be tested to support possible safety assessments, if necessary. Additional details are provided in the study procedures manual (SPM).

Overview of Study Design and Key Features

Figure 2 Study design overview – Infant participants

AESI = adverse event of special interest; **MAE** = medically attended adverse event; **RTI** = respiratory tract illness; **(S)AE** = (serious) adverse event

Infant sub-cohorts are abbreviated “BS1”, “BS2” and “BS3” correspond to Visit 2-NB (Day 43 post-birth), Visit 3-NB (Day 121 post-birth) and Visit 4-NB (Day 181 post-birth), respectively.

RSV_MAT_BS1, _BS2, _BS3 = infants born to women in the RSV_MAT group and evaluated for immunogenicity at the designated timepoint (Day 43, Day 121 or Day 181 post-birth).

Control_BS1, _BS2, _BS3 = infants born to women in the Control group evaluated for immunogenicity at the designated timepoint (Day 43, Day 121 or Day 181 post-birth)

¹ If cord blood was not collected at delivery/birth, a blood sample should be collected from the infant within 72 hours post-birth.

² Any neonatal / infant AESIs identified after 42 days post-birth should also be reported.

³ **Due to the change in the study requirements, there will no longer be collection of blood samples at Visit 2-NB, Visit 3-NB and Visit 4-NB.**

Note:
An additional recommended safety contact may be performed ~7 days post-birth if deemed necessary by the investigator or by the parent/ LAR(s).

Design Features	
Study Type: self-contained.
 
Experimental design: Phase III, double-blind*, randomized, placebo-controlled, multi-center, multi-country study with 1 investigational RSV MAT vaccine group in a parallel design.
 
* Due to the recent safety signal, the study was fully unblinded to ensure the safety monitoring of the participants.
 
Study Population: High risk pregnant women aged 15 to 49 years and infants born to the vaccinated mothers.

------------------------	--

Overview of Study Design and Key Features	
	
Duration of the study: The intended duration of the study for maternal participant is approximately 10 to 11 months (including screening visit, from informed consent/assent until 180 days post-delivery) and approximately 12 months for infant participants (from birth until 365 days post-birth), which is expected to cover at least 1 complete RSV season.
 
Control: Placebo control.
 
Blinding: Double-blind*, as described in Table 2.
 
* Due to the recent safety signal, the study was fully unblinded to ensure the safety monitoring of the participants.

Study intervention	
Study (intervention) groups are single 120 µg dose of the investigational RSV vaccine and Placebo control, as described in Table 2.

Study intervention Assignment	
Study intervention schedule*: 1 single dose administered IM between 24 and 36 weeks of gestation (at Visit 1, Day 1) to maternal participants.
 
* Due to the recent safety signal, there will be no further enrollment and vaccination of maternal participants.
 
Randomized study intervention allocation* is 2:1 (investigational vaccine: placebo), as described in Table 2.
 
* Due to the recent safety signal, there will be no further enrollment and vaccination of maternal participants.

Conduct of Analyses	
No analysis requiring statistical adjustment will be performed. However, analyses to evaluate objectives and endpoints will be performed in steps. Refer to Section 4.7 for details.

CONFIDENTIAL

Table 2 Study groups, intervention and blinding

Study groups	Maternal participants				Infant participants		Sub-cohorts for randomization (Allocation 1:1:1)	Blinding		
	~Number	Age in years (Min-Max)	Intervention name	Study groups for randomization (Allocation 2:1)	Infant Blood Sampling sub-cohorts			M + I Up to Day 43 post-delivery/birth	M + I Up to Day 181 post-delivery/birth	I only From Day 182 to Day 366 post-delivery/birth
					Name	~Number		Double-blind**	Single-blind**	Single-blind**
RSV_MAT	~252 *	15 – 49	RSV MAT	RSV_MAT	RSV_MAT_BS1	~84	RSV_MAT_BS1	•	•	•
					RSV_MAT_BS2	~84	RSV_MAT_BS2			
					RSV_MAT_BS3	~84	RSV_MAT_BS3			
Control	~126 *	15 – 49	Control	Control	Control_BS1	~42	Control_BS1	•	•	•
					Control_BS2	~42	Control_BS2			
					Control_BS3	~42	Control_BS3			

Control = Placebo; **M** = maternal participants; **I** = infant participants

Infant sub-cohorts are abbreviated “BS1”, “BS2” and “BS3” correspond to Visit 2-NB (Day 43 post-birth), Visit 3-NB (Day 121 post-birth) and Visit 4-NB (Day 181 post-birth), respectively.

RSV_MAT_BS1, _BS2, _BS3 = infants born to women in the RSV_MAT group and evaluated for immunogenicity at the designated timepoint (Day 43, Day 121 or Day 181 post-birth).

Control_BS1, _BS2, _BS3 = infants born to women in the Control group evaluated for immunogenicity at the designated timepoint (Day 43, Day 121 or Day 181 post-birth)

* The double-blinding will apply from Day 1 pre-study intervention to Day 43 post-delivery/birth visit after which the first analysis will be conducted and treatment-level unblinded summaries will be provided to GSK and regulatory agency for review. No individual treatment code will be shared with investigators, site staff and participants until the end of the study

* **Due to the recent safety signal in RSV-MAT-009, there will be no further enrollment and vaccination of maternal participants.**

** **Due to the recent safety signal, the study was fully unblinded to ensure the safety monitoring of the participants**

2. STATISTICAL HYPOTHESES

No statistical hypotheses will be tested. All statistical analyses are descriptive.

2.1. Multiplicity Adjustment

No analysis requiring statistical adjustment will be performed.

3. ANALYSIS SETS

3.1. Definition

Table 3 Maternal Participants

Analysis Set	Definition / Criteria	Analyses Evaluated
Enrolled	All maternal participants who completed the informed consent process and signed the informed consent form and were determined as eligible for study participation.	Study Population
Exposed	All maternal participants who received 1 dose of a study intervention. The allocation in a group is done in function of the administered intervention.	Safety
Full Analysis Immunogenicity	All maternal participants in the Exposed set who have at least one post-dosing immunogenicity data. It will be defined by timepoint, e.g. FAS at Day 31	Immunogenicity
Per-Protocol Immunogenicity	All maternal participants in the Full Analysis (Immunogenicity) minus participants with protocol deviations that lead to exclusion. The analysis will be done according to the study interventions that participants received. It will be defined by timepoint, e.g. PPS at Day 31.	Immunogenicity
Solicited Safety	All maternal participants in the Exposed set who have solicited safety data.	Safety

FAS = Full Analysis Set; PPS = Per Protocol Set

Table 4 Infant Participants

Analysis Set	Definition / Criteria	Analyses Evaluated
Exposed	Infants live-born to exposed maternal participants, whose parents/LARs completed the informed consent process and signed the informed consent form.	Safety
Full Analysis Immunogenicity	All infant participants in the Exposed set who have at least one post-delivery/birth immunogenicity data. The analysis will be done according to the study intervention that maternal participants received. It will be defined by timepoint, e.g. FAS at Day 31	Immunogenicity
Per-Protocol Immunogenicity	All infant participants in the Full Analysis (Immunogenicity) set minus those who (a) were born less than 4 weeks post-maternal participant dosing and/ or (b) have protocol deviations that lead to exclusion. It will be defined by timepoint, e.g. PPS at Day 31	Immunogenicity

FAS = Full Analysis Set; PPS = Per Protocol Set

3.2. Criteria for eliminating data from Analysis Sets

Elimination codes are used to identify participants to be eliminated from analysis. Detail is provided below for each set.

3.2.1. Elimination from Exposed Set (ES)

Maternal participants: Code 1030 (Study vaccine not administered at all), 800 (Fraudulent data) and code 900 (invalid informed consent) will be used for identifying maternal participants eliminated from ES.

Infants: Code 1030 (Study vaccine not administered at all, carry forward elimination from mother to infant), 800 (Fraudulent data), code 900 (invalid informed consent) and code 901 (invalid informed consent due to mother) will be used for identifying infants eliminated from ES.

3.2.2. Elimination from Full Analysis Set (FAS) - Immunogenicity

3.2.2.1. Excluded participants from FAS of maternal participants

A maternal participant will be excluded from the FAS analysis under the following conditions.

Table 5 Elimination code and condition for maternal participants

Code	Condition under which the code is used	Visit (timepoints) where the code is applicable	Applicable for analysis set/endpoint
800	Fraudulent data	All	All
900	Invalid informed consent	All	All
1030	Study vaccine not administered at all	All	Safety, immunogenicity
2100.Vx	Serological results not available post-vaccination	Visit 2/Day 31, Visit 3/Delivery	Immunogenicity

Vx indicates participants whose immunogenicity data will be eliminated from a specific visit.

3.2.2.2. Excluded participants from FAS of infant participants

An infant participant will be excluded from the FAS analysis under the following conditions.

Table 6 Elimination code and condition for infant participants

Code	Condition under which the code is used	Visit (timepoints) where the code is applicable	Applicable for analysis set/endpoint
800	Fraudulent data	All	All
900	Invalid informed consent	All	All
901#	Invalid informed consent - mother	All	All
1030#	Study vaccine not administered at all - mother	All	Safety, immunogenicity
2100.Vx	Serological results not available	Visit 1-NB/Birth* Visit 2-NB/Day 43 post-birth Visit3-NB/Day 121 post-birth Visit4-NB/Day 181 post-birth	Immunogenicity

#Carry forward elimination from mother to infant

Vx indicates participants whose immunogenicity data will be eliminated from a specific visit.

*cord blood sample or blood sample collected within 72 hours after birth if cord blood sample is not collected

3.2.3. Elimination from Per-protocol analysis Set (PPS) - Immunogenicity

3.2.3.1. Excluded participants from Per-protocol analysis set of maternal participants

A maternal participant will be excluded from the PPS analysis under the following conditions.

Table 7 Elimination code and condition for maternal participants

Code	Condition under which the code is used	Visit (timepoints) where the code is applicable	Applicable for analysis set/endpoint
800	Fraudulent data	All	All
900	Invalid informed consent	All	All
1030	Study vaccine not administered at all	All	Safety, immunogenicity
1040.Vx+*	Administration of concomitant vaccine(s) forbidden in the protocol	Visit 2/Day 31, Visit 3/Delivery	Immunogenicity
1050	Randomisation failure	All	Immunogenicity
1060	Randomisation code was broken	All	Immunogenicity
1070**	Participants got vaccinated with the correct vaccine but containing an incorrect volume	All	Immunogenicity
1070**	Vaccination not according to protocol (site of injection, route of administration, wrong replacement of study treatment administered)	All	Immunogenicity
1070**	Study treatment not prepared as per protocol (e.g. reconstitution)	All	Immunogenicity
1070**	Other deviations related to wrong study treatment/administration/dose	All	Immunogenicity
1070**	Study treatment administered while contraindication	All	Immunogenicity
1080	Vaccine temperature deviation	All	Immunogenicity
1090	Expired vaccine administered	All	Immunogenicity

CONFIDENTIAL

Code	Condition under which the code is used	Visit (timepoints) where the code is applicable	Applicable for analysis set/endpoint
2010	Protocol violation (inclusion/exclusion criteria) DOB – VAC – 15-49 years Gestational age at vaccination - 28 ^{0/7} - 36 ^{0/7}	All	Immunogenicity
2040.Vx+*	Administration of any medication forbidden by the protocol	Visit 2/Day 31, Visit 3/Delivery	Immunogenicity
2040.Vx+*	Device, excluded by the protocol, was administered	Visit 2/Day 31, Visit 3/Delivery	Immunogenicity
2050.Vx+*	Intercurrent medical conditions which are exclusionary as per protocol	Visit 2/Day 31, Visit 3/Delivery	Immunogenicity
2060.Vx+*	Concomitant infection related to the vaccine which may influence immune response	Visit 2/Day 31, Visit 3/Delivery	Immunogenicity
2070.Vx+*	Concomitant infection not related to the vaccine but may influence immune response	Visit 2/Day 31, Visit 3/Delivery	Immunogenicity
2090.Vx	Subjects did not comply with blood sample schedule: 
 • For PPS at Day 31, check the interval from vaccination to day 31 BS = 20 – 45 days; • For PPS at Delivery, check the interval from delivery to delivery BS = 1 day before to 3 days after delivery; 	Visit 2/Day 31, Visit 3/Delivery	Immunogenicity
2100.Vx	Serological results not available post-vaccination	Visit 2/Day 31, Visit 3/Delivery	Immunogenicity
2120.Vx	Obvious incoherence or abnormality or error in data	Visit 2/Day 31, Visit 3/Delivery	Immunogenicity
2130.Vx	Testing performed on samples not aligned with ICF	Visit 2/Day 31, Visit 3/Delivery	Immunogenicity

*Attribution of these elimination codes to subject need CRDL review of individual listing

** Attribution of code 1070 to a subject requires CRDL confirmation

Vx+ indicates subjects whose immunogenicity data will be eliminated from a specific visit onwards; Vx indicates subjects whose immunogenicity data will be eliminated from a specific visit.

DOB-Date of Birth, VAC-Vaccination, BS- Blood Sample

BS- Blood Sample.

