3.2.3.2. Excluded participants from Per-protocol analysis set of infant participants

An infant participant will be excluded from the PPS analysis under the following conditions.

Table 8 Elimination code and condition for infant participants

Code	Condition under which the code is used	Visit (timepoints) where the code is applicable	Applicable for analysis set/endpoint
800	Fraudulent data	All	All
900	Invalid informed consent - infant	All	All
901#	Invalid informed consent - mother	All	All
1030#	Study vaccine not administered at all	All	Safety, immunogenicity
1040.Vx+*	Administration of concomitant vaccine(s) forbidden in the protocol - infant	Visit 2-NB/Day 43 post-birth Visit3-NB/Day 121 post-birth Visit4-NB/Day 181 post-birth	Immunogenicity
1041#*	Maternal administration of concomitant vaccine(s) forbidden in the protocol up to Delivery	All	Immunogenicity
1050#	Maternal randomisation failure	All	Immunogenicity
1060#	Maternal randomisation code was broken	All	Immunogenicity
1070#	Maternal participants got vaccinated with the correct vaccine but containing an incorrect volume	All	Immunogenicity
1070#	Vaccination not according to protocol (site of injection, route of administration, wrong replacement of study treatment administered)	All	Immunogenicity
1070#	Study treatment not prepared as per protocol (e.g. reconstitution)	All	Immunogenicity
1070#	Other deviations related to wrong study treatment/administration/dose	All	Immunogenicity

CONFIDENTIAL

Code	Condition under which the code is used	Visit (timepoints) where the code is applicable	Applicable for analysis set/endpoint
1070#	Study treatment administered while contraindicated	All	Immunogenicity
1080#	Vaccine temperature deviation	All	Immunogenicity
1090#	Expired vaccine administered	All	Immunogenicity
2010	Protocol violation (inclusion/exclusion criteria) - infant	All	Immunogenicity
2011#	Protocol violation (inclusion/exclusion criteria) - mother	All	Immunogenicity
2040.Vx+*	Administration of any medication forbidden by the protocol - infant	Visit 2-NB/Day 43 post-birth Visit3-NB/Day 121 post-birth Visit4-NB/Day 181 post-birth	Immunogenicity
2040.Vx+*	Device, excluded by the protocol, was administered - infant	Visit 2-NB/Day 43 post-birth Visit3-NB/Day 121 post-birth Visit4-NB/Day 181 post-birth	Immunogenicity
2041#*	Maternal administration of any medication forbidden by the protocol up to Delivery	All	Immunogenicity

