2130.Vx	Testing performed on samples not aligned with ICF	Visit 1-NB/Birth Visit 2-NB/Day 43 post-birth Visit3-NB/Day 121 post-birth Visit4-NB/Day 181 post-birth	Immunogenicity
3100	Delivery happens less than 4 weeks post vaccination	All	Immunogenicity

*Attribution of these elimination codes to subject need CRDL review of individual listing

#Carry forward elimination from mother to infant

Vx+ indicates subjects whose immunogenicity data will be eliminated from a specific visit onwards; Vx indicates subjects whose immunogenicity data will be eliminated from a specific visit.

BS- Blood Sample.

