6.1.3. Protocol Deviations

Important protocol deviations will be summarized based on Exposed Set by group.

Protocol deviations will be tracked by the study team throughout the conduct of the study. These protocol deviations will be reviewed to identify those considered as important as follows:

- Data will be reviewed prior to unblinding and freezing the database to ensure all important deviations (where possible without knowing the study intervention details) are captured and categorised in the protocol deviations dataset.
- This dataset will be the basis for the summaries of important protocol deviations.
- The summary will include number and percentage of participants with important protocol deviations by deviation category for each study group.
- An individual listing of protocol deviation will also be provided.

Protocol deviations which result in exclusion from the analysis set will also be summarized based on Exposed Set by group.

- Data will be reviewed prior to unblinding and freezing the database to ensure all deviations leading to analysis population exclusions are captured and categorised in the protocol deviations ADaM dataset (note these exclusions are not captured in the SDTM dataset).

In addition to the overall summary of important protocol deviations, separate summaries may be produced for important protocol deviations related to COVID-19, and important protocol deviations not related to COVID-19 respectively if deemed necessary.

Summary of important protocol deviations leading to elimination will be tabulated by group. An individual listing will also be provided.

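### The SAP records full unblinding, yet requires per-protocol exclusions to be reviewed before unblinding and does not limit code 1060 to individual code breaks

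*SAP*

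**What the plan says.** **Unblinding.** SAP section 1.2, in the design description and again under Table 2, states that the study was fully unblinded because of the safety signal. Protocol Amendment 1 (15 March 2022) already reports this in the past tense, and its summary of changes says the study team was unblinded while assessing the safety issue. SAP Amendment 1 is dated 1 June 2022 and was written to align with that protocol amendment.

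**Exclusion review.** SAP 6.1.3 says: "Data will be reviewed prior to unblinding and freezing the database to ensure all deviations leading to analysis population exclusions are captured". A separate bullet on important deviations is softened by "where possible without knowing the study intervention details". The bullet on exclusions has no such qualifier.

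**Code breaks.** SAP Table 7 lists code 1060, "Randomisation code was broken", among the conditions under which a mother will be excluded from the PPS. It applies to immunogenicity at all visits. Table 8 carries it to the infant as 1060#: "Maternal randomisation code was broken". Neither entry has a definition, a date limit or a mark for case review.

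**Who decides.** Both tables footnote a group of codes with "Attribution of these elimination codes to subject need CRDL review of individual listing". Table 7 adds "Attribution of code 1070 to a subject requires CRDL confirmation". Protocol 8.2.3.1 names the CRDL as a core member of the Safety Review Team.

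**Use of the set.** SAP 4.2.2.1 makes the PPS the basis of the primary immunogenicity analysis, with delivery and birth as the primary post-dose timepoints. SAP 4.1 requires a complementary full analysis set (FAS) analysis only if exclusions reach 5% or more in some group at some timepoint.

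**The concern.** Reviewing exclusions before unblinding keeps knowledge of the arm from influencing who enters the per-protocol set. Here the unblinding came first for any participant who had not yet delivered. For those participants the written safeguard cannot operate, and the SAP puts nothing in its place. Where a code leaves room for judgement, a reviewer who knows the arm could apply it differently in the two groups, at the primary timepoint and in the primary set.

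The unqualified code 1060 is a second gap of the same origin. A document that says the whole study was unblinded and also says that a broken code excludes a participant should state that the first event does not trigger the second.

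**Working it through.** **1. The plan's own figures.** Evaluable mothers in the vaccine group: 252 x (1 - 0.10) = 226.8, stated as 226. Overall: 378 x 0.90 = 340.2, stated as 340. Both reproduce, and neither changes here.

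**2. Could primary-timepoint data arise after unblinding?** Inputs:
- Unblinding: 15 March 2022 at the latest (Protocol Amendment 1).
- Last dosing: no later than 25 February 2022. Protocol 2.3 gives that as the stop date and describes an earlier pause without dating it, so this is an upper bound.
- Gestational age at dosing: protocol 5.1.1 allows 24 to 36 weeks, while SAP code 2010 prints 28 to 36 weeks.
- Assumption: delivery at 37 to 40 weeks.

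Delivery date = 25 February 2022 + (weeks at delivery - weeks at dosing) x 7 days.

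| Dosed at | Delivery at 37 weeks | Delivery at 40 weeks | Latest, days after 15 March |
|---|---|---|---|
| 36 weeks | +7 d = 4 March | +28 d = 25 March | 10 |
| 28 weeks | +63 d = 29 April | +84 d = 20 May | 66 |
| 24 weeks | +91 d = 27 May | +112 d = 17 June | 94 |

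The 28-week row is consistent with both documents. Under code 2010 as printed, the woman in the 24-week row would be removed from the PPS anyway. The two gestational-age windows must be reconciled, but this point does not depend on which one stands.

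**3. How many codes pass through the CRDL?** Table 7 has 18 distinct codes: 800, 900, 1030, 1040, 1050, 1060, 1070, 1080, 1090, 2010, 2040, 2050, 2060, 2070, 2090, 2100, 2120, 2130. Six are marked for CRDL review or confirmation: 1040, 1070, 2040, 2050, 2060, 2070. All six apply at delivery. Maternal counterparts reach the infant through Table 8, for example code 1041#: "Maternal administration of concomitant vaccine(s) forbidden in the protocol up to Delivery".

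**4. Two readings of code 1060.**
- Individual breaks only: it removes those participants, and the study-level unblinding has no effect on the PPS.
- Literal: every code has been broken, so the PPS is 0 of about 252 and 0 of about 126 planned (100% excluded). The 5% trigger is met and the FAS becomes the only immunogenicity analysis with data. FAS Tables 5 and 6 do not list code 1060.

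**5. How far could arm-dependent exclusion move a result without triggering the FAS analysis?** At planned numbers the trigger is 13 of 252 (5.2%) or 7 of 126 (5.6%). Take the limiting 5%, the SAP's log10 SD of 0.4, normal log titres, and the extreme case in which exactly the lowest 5% of vaccine titres are removed:
- Shift in log10 mean = 0.4 x 0.103 / 0.95 = 0.043 (0.103 is the standard normal density at the 5% point), or 10^0.043 = about 1.10-fold.
- Also removing the highest 5% of control titres doubles the log shift to about 0.087, or about 1.22-fold in the between-group ratio.
- The SAP anticipates a 9- to 12-fold rise in RSV-A neutralizing titre.

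**The case against.** **Code 1060 plainly means individual breaks.** That is the likely intent. The PPS removes participants with protocol deviations, and a sponsor decision recorded in an amendment is not one. Protocol 6.3.5.1 and 6.3.5.2 treat individual unblinding separately. A reader might infer that the plan will empty its own primary set; the documents do not say that. What stands is that the text does not exclude that reading.

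**Unblinding in 6.1.3 may mean release of codes for the analysis.** The SAP does not define it so, and this would not mask a reviewer who already has access to treatment. The other half of the same sentence, review before the database is frozen, can still be met.

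**Most of the six codes are not discretionary.** Largely accepted. Codes 1040 and 2040 concern products the protocol forbids, 2050 refers to protocol-defined conditions, and 1070 mostly concerns volume, route, site and preparation. Code 2070, on infections unrelated to the vaccine that might affect the response, is the clearest matter of judgement. Six of 18 counts codes, not discretion or affected participants.

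**The consequence is small.** Also largely accepted. No hypothesis is tested, protocol 6.3.5 keeps the testing laboratory blinded, and the extreme case in step 5 needs a reviewer who knows titres as well as arm. Two things remain. Laboratory blinding protects assay values, not the decision on who enters the PPS. And the planned 10% non-evaluable rate does not guarantee the FAS analysis, because a missing sample is not a result excluded from the PPS.

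**Conclusion.** The point holds and should be fixed. The exclusion-review rule in 6.1.3 cannot be met for any delivery after the study-level unblinding, and codes 1060/1060# lack a limit that they need once the whole study is unblinded.

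The size is bounded. Below the FAS trigger, even extreme selection would shift the vaccine geometric mean by about 1.10-fold, or the between-group ratio by about 1.22-fold, assuming a log10 SD of 0.4 and normal log titres.

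Three stronger conclusions are tempting and unsupported. The documents show no biased exclusion. They do not show that primary samples fell after SAP Amendment 1; that needs dosing at 24 weeks close to 25 February 2022, which code 2010 as printed would exclude and the undated pause makes uncertain. And they do not show that the CRDL assigned any code with knowledge of the arm, only that the SAP no longer prevents it.

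The timing rests on dosing up to the stop date and delivery at 37 to 40 weeks. The documents do not give the number still pregnant at unblinding, the number of individual code breaks, or actual enrolment.

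**What to change.** 1. Add a footnote to Tables 7 and 8: codes 1060 and 1060# apply only to individual participant-level code breaks, and the sponsor's study-level unblinding is not an elimination.
2. In 6.1.3, for PPS exclusions, replace review before unblinding with review and freezing of exclusions before database lock, from listings that omit treatment group and antibody results. Exempt codes that cannot be judged that way: those that need the allocation (1050, and 1070 for a wrong treatment) or the assay value (2120, "Obvious incoherence or abnormality or error in data").

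The cost is SAP wording and a little work to prepare masked listings, with no new data or procedures. The change helps only if made before the exclusions are decided.
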